5.1 Child-Pugh Classification

Hepatic impairment is classified using the Child-Pugh system. The classification parameters will be collected at screening to determine the CP class for each subject prior to tirzepatide dose administration ([Table GPGQ.1](#)).

Table GPGQ.1. Child-Pugh Classification

Parameter	1 point	2 points	3 points
Serum Albumin (g/dL)	>3.5	2.8 to 3.5	<2.8
Total Serum Bilirubin (mg/dL)	<2	2 to 3	>3
Prothrombin Time (sec. prolonged) or	<4	4 to 6	>6
Prothrombin Time INR	<1.7	1.7 to 2.3	>2.3
Ascites ^a	Absent	Slight	Moderate
Hepatic Encephalopathy ^b	None	1 or 2 Or current treatment with lactulose or neomycin or other antibiotics	3 or 4 Or continued encephalopathy while receiving treatment with lactulose and/or neomycin or other antibiotics

Child Pugh A (mild): 5 or 6 points; Child Pugh B (moderate): 7 to 9 points; Child Pugh C (severe): 10 to 15 points. Adapted from Child and Turcotte³ and Pugh et al.⁴

Abbreviations: INR = international normalized ratio.

^a Absent: no detectable ascites.

Slight: no distension; ascites are only detectable by ultrasound examination.

Moderate: ascites causing moderate symmetrical distension of the abdomen.

^b Grade 0: normal consciousness, personality, neurological examination, electroencephalogram.

Grade 1: restless, sleep disturbed, irritable/agitated, tremor, impaired handwriting, 5 cycles per second waves.

Grade 2: lethargic, time-disoriented, inappropriate, asterixis, ataxia, slow triphasic waves.

Grade 3: somnolent, stuporous, place-disoriented, hyperactive reflexes, rigidity, slower waves.

Grade 4: unrousable coma, no personality/behavior, decerebrate, slow 2 to 3 cycles per second delta activity.

6. TREATMENTS

The TFLs will include a subheader for treatment (5 mg tirzepatide SC) throughout. The following is a list of the group abbreviations that will be used in the TFLs.

Group	Order in TFL
Control (normal hepatic function)	1
Mild hepatic impairment	2
Moderate hepatic impairment	3
Severe hepatic impairment	4

7. SAMPLE SIZE JUSTIFICATION

It is planned that up to 30 subjects may be enrolled. To support the planned analyses, at least 6 subjects in the mild and moderate hepatic impairment groups (Groups 2 and 3), at least 6 and up to 12 control subjects (Group 1) are expected to complete the study. Efforts will be made to achieve 6 completers with severe hepatic impairment (Group 4); however, acknowledging the difficulty in recruiting this subject population, 2 to 3 subjects with severe hepatic impairment may be an acceptable target.

This sample size is based on the FDA guidance⁵, which advises that at least 6 subjects in each study arm (group) are required to provide evaluable data. The sample size was not selected to satisfy an a priori statistical requirement.

8. DEFINITION OF ANALYSIS POPULATIONS

The “Safety” population will consist of all enrolled subjects, whether or not they completed all protocol requirements.

The “Pharmacokinetic” population will consist of all subjects who received tirzepatide and have evaluable PK data.

The “Pharmacodynamic” population will consist of all subjects who received tirzepatide and have evaluable PD data.

All protocol deviations that occur during the study will be considered for their severity/impact and will be taken into consideration when subjects are assigned to analysis populations.

9. STATISTICAL METHODOLOGY

9.1 General

Data listings will be provided for all data that is databased. Summary statistics and statistical analysis will only be presented for data where detailed in this SAP. For continuous data, summary statistics will include the arithmetic mean, arithmetic standard deviation (SD), median, min, max and N; for log-normal data (e.g. the PK parameters: area under the concentration versus time curve [AUC] and maximum observed drug concentration [C_{max}]) the geometric mean and geometric coefficient of variation (CV%) will also be presented. For categorical data, frequency count and percentages will be presented. Data listings will be provided for all subjects up to the point of withdrawal, with any subjects excluded from the relevant population highlighted. Summary statistics and statistical analyses will generally only be performed for subjects included in the relevant analysis population. For the calculation of summary statistics and statistical analysis, unrounded data will be used.

Mean change from baseline is the mean of all individual subjects' change from baseline values. Each individual change from baseline will be calculated by subtracting the individual subject's baseline value from the value at the timepoint. The individual subject's change from baseline values will be used to calculate the mean change from baseline using a SAS procedure such as Proc Univariate.

Data analysis will be performed using SAS[®] Version 9.4 or greater.

9.2 Demographics and Subject Disposition

Subject disposition will be listed. The demographic variables age, sex, race, ethnicity, country of enrolment, site ID, body weight, height, body mass index, and Child-Pugh score will be summarized by group and listed. All other demographic variables will be listed only.

9.3 Pharmacokinetic Assessment

9.3.1 Pharmacokinetic Analysis

The PK parameter estimates will be determined using non-compartmental procedures in validated software program (Phoenix WinNonlin Version 8.1 or later).

Plasma concentrations of tirzepatide will be used to determine the following PK parameters, when possible:

Parameter	Units	Definition
AUC(0-t _{last})	h*ng/mL	area under the concentration versus time curve from time zero to time t, where t is the last time point with a measurable concentration
AUC(0-∞)	h*ng/mL	area under the concentration versus time curve from time zero to infinity
%AUC(t _{last} -∞)	%	percentage of AUC(0-∞) extrapolated
C _{max}	ng/mL	maximum observed drug concentration
t _{max}	h	time of maximum observed drug concentration
t _½	h	half-life associated with the terminal rate constant (λ_z) in non-compartmental analysis
CL/F	L/h	apparent total body clearance of drug calculated after extra-vascular administration
V _{Z/F}	L	apparent volume of distribution during the terminal phase after extra-vascular administration
V _{SS/F}	L	apparent volume of distribution at steady state after extra-vascular administration

Additional PK parameters may be calculated, as appropriate.

The software and version used for the final analyses will be specified in the clinical study report. Any exceptions or special handling of data will be clearly documented within the final study report.

Formatting of tables, figures and abbreviations will follow the Eli Lilly Global PK/PD/TS Tool: NON-COMPARTMENTAL PHARMACOKINETIC STYLE GUIDE. The version of the tool effective at the time of PK analysis will be followed.

General PK Parameter Rules

- Actual sampling times will be used in the final analyses of individual PK parameters, except for pre-dose sampling times which will be set to zero.
- C_{max} and t_{max} will be reported from observed values. If C_{max} occurs at more than one time point, t_{max} will be assigned to the first occurrence of C_{max}.

- AUC parameters will be calculated using a combination of the linear and logarithmic trapezoidal methods (linear-log trapezoidal rule). The linear trapezoidal method will be applied up to t_{max} and then the logarithmic trapezoidal method will be used after t_{max} . The minimum requirement for the calculation of AUC will be the inclusion of at least three consecutive concentrations above the lower limit of quantitation (LLOQ), with at least one of these concentrations following C_{max} .
- AUC(0-∞) values where the percentage of the total area extrapolated is more than 20% will be flagged. Any AUC(0-∞) value excluded from summary statistics will be noted in the footnote of the summary table.
- Half-life ($t_{1/2}$) will be calculated, when appropriate, based on the apparent terminal log-linear portion of the concentration-time curve. The start of the terminal elimination phase for each subject will be defined by visual inspection and generally will be the first point at which there is no systematic deviation from the log-linear decline in plasma concentrations. Half-life will only be calculated when a reliable estimate for this parameter can be obtained comprising of at least 3 data points. If $t_{1/2}$ is estimated over a time window of less than 2 half-lives, the values will be flagged in the data listings. Any $t_{1/2}$ value excluded from summary statistics will be documented in the footnote of the summary table.
- A uniform weighting scheme will be used in the regression analysis of the terminal log-linear portion of the concentration-time curve.
- The parameters based on the predicted last quantifiable drug concentration (C_{last}) will be reported.

Individual PK Parameter Rules

- Only quantifiable concentrations will be used to calculate PK parameters with the exception of special handling of certain concentrations reported below the lower limit of quantitation (BQL). Plasma concentrations reported as BQL will be set to a value of zero when all of the following conditions are met:
 - The compound is non-endogenous.
 - The samples are from the initial dose period for a subject or from a subsequent dose period following a suitable wash-out period.
 - The time points occur before the first quantifiable concentration.
- All other BQL concentrations that do not meet the above criteria will be set to missing.
- Also, where two or more consecutive concentrations are BQL towards the end of a profile, the profile will be deemed to have terminated and therefore any further quantifiable concentrations will be set to missing for the calculation of the PK parameters unless it is considered to be a true characteristic of the profile of the drug.

Individual Concentration vs. Time Profiles

- Individual concentrations will be plotted utilizing actual sampling times.
- The terminal point selections will be indicated on a semi-logarithmic plot.

Average Concentration vs. Time Profiles

- The average concentration profiles will be graphed using scheduled (nominal) sampling times.
- The average concentration profiles will be graphed using arithmetic average concentrations.
- The pre-dose average concentration for single-dose data from non-endogenous compounds will be set to zero. Otherwise, only quantifiable concentrations will be used to calculate average concentrations.
- Concentrations at a sampling time exceeding the sampling time window specified in the protocol, or $\pm 10\%$, will be excluded from the average concentration profiles.
- Concentrations excluded from the mean calculation will be documented in the final study report.
- A concentration average will be plotted for a given sampling time only if 2/3 of the individual data at the time point have quantifiable measurements that are within the sampling time window specified in the protocol or $\pm 10\%$. An average concentration estimated with less than 2/3 but more than 3 data points may be displayed on the mean concentration plot if determined to be appropriate and will be documented within the final study report.

Treatment of Outliers during Pharmacokinetic Analysis

Application of this procedure to all PK analyses is not a requirement. Rather, this procedure provides justification for exclusion of data when scientifically appropriate. This procedure describes the methodology for identifying an individual value as an outlier for potential exclusion, but does not require that the value be excluded from analysis. The following methodology will not be used to exclude complete profiles from analysis.

Data within an Individual Profile

A value within an individual profile may be excluded from analysis if any of the following criteria are met:

- For PK profiles during single dosing of non-endogenous compounds, the concentration in a pre-dose sample is quantifiable.

- For any questionable datum that does not satisfy the above criteria, the profile will be evaluated and results reported with and without the suspected datum.

Data between Individual Profiles

1. If $n < 6$, then the dataset is too small to conduct a reliable range test. Data will be analyzed with and without the atypical value, and both sets of results will be reported.
2. If $n \geq 6$, then an objective outlier test will be used to compare the atypical value to other values included in that calculation:
 - a. Transform all values in the calculation to the logarithmic domain.
 - b. Find the most extreme value from the arithmetic mean of the log transformed values and exclude that value from the dataset.
 - c. Calculate the lower and upper bounds of the range defined by the arithmetic mean $\pm 3*SD$ of the remaining log-transformed values.
 - d. If the extreme value is within the range of arithmetic mean $\pm 3*SD$, then it is not an outlier and will be retained in the dataset.
 - e. If the extreme value is outside the range of arithmetic mean $\pm 3*SD$, then it is an outlier and will be excluded from analysis.

If the remaining dataset contains another atypical datum suspected to be an outlier and $n \geq 6$ following the exclusion, then repeat step 2 above. This evaluation may be repeated as many times as necessary, excluding only one suspected outlier in each iteration, until all data remaining in the dataset fall within the range of arithmetic mean $\pm 3*SD$ of the log-transformed values.

Reporting of Excluded Values

Individual values excluded as outliers will be documented in the final report. Approval of the final report will connote approval of the exclusion.

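### SAP 9.3.1 makes outlier deletion both optional and mandatory, leaves the comparison set open, and requires no with-and-without result at n ≥ 6, where the test flags about 31% of clean groups of 6

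*SAP*

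**What the plan says.** The outlier text is in SAP 9.3.1, under Treatment of Outliers during Pharmacokinetic Analysis.

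- **Preamble.** "Application of this procedure to all PK analyses is not a requirement". "Rather, this procedure provides justification for exclusion of data when scientifically appropriate". The method identifies a value for possible exclusion "but does not require that the value be excluded from analysis". It is also not to be used to remove complete profiles.
- **Between profiles, n < 6.** The data are considered too few for a reliable range test. "Data will be analyzed with and without the atypical value, and both sets of results will be reported".
- **Between profiles, n ≥ 6.** "an objective outlier test will be used to compare the atypical value to other values included in that calculation". Values are log-transformed, the most extreme is set aside, and mean ± 3 SD is computed from the rest. If the extreme value lies outside that range, "then it is an outlier and will be excluded from analysis". The step may be repeated while at least six values remain.
- **Reporting.** Excluded values are documented in the final report. "Approval of the final report will connote approval of the exclusion".

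SAP 9.3.2 fits the primary ANCOVA to log AUC(0-∞) and Cmax, with group and body weight. SAP 5 plans at least 6 subjects in each of Groups 1 to 3 and up to 6 in Group 4. SAP 7 adds that "2 to 3 subjects with severe hepatic impairment may be an acceptable target".

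**The concern.** There are three separate faults.

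1. **Contradiction.** The preamble says a flagged value need not be excluded; the final step says it will be. Two analysts could follow the same SAP and report different primary results.
2. **Comparison set.** The set is tied only to the calculation in hand. A group summary has about 6 values; the ANCOVA has 20 or more (6+6+6+2 = 20, up to 30). Group by group, a severe group of 2 to 3 is not tested and both results are reported. Pooled, the same subjects are tested against everyone else and lose that reporting.
3. **Reporting.** At n ≥ 6 no primary result that includes the excluded values is required, although this is where the test flags often.

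The values at risk are the primary endpoints of an open-label study. The practical harms are intervals that cover less than stated and deletion at the analyst's discretion. Under the pooled reading, the rule can also remove subjects from the very group that carries an effect.

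**Working it through.** The SAP states no error rate for this test, so there is no plan figure to reproduce. No CV is given either; every CV below is an assumption. The flag rate on clean data does not depend on the CV.

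**Flag rate on clean data.** Take n independent normal log values, remove one, and let m and s be the mean and sample SD of the other n−1. Then (x − m) / (s√(1 + 1/(n−1))) follows t with n−2 df. Being outside m ± 3s therefore means |t| > 3/√(1 + 1/(n−1)), and over n candidate values

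P(flag) ≤ n × 2 × P(t(n−2) > 3/√(1 + 1/(n−1))).

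For n = 6 the cut is 3/√1.2 = 2.739 on 4 df, the one-sided tail is 0.02599, and 6 × 2 × 0.02599 = 0.312. At n = 6 the bound is exact. The limit corresponds to a deviation of 1.649 overall SDs; two such values would need 2 × 1.649² = 5.44, more than the available n−1 = 5, so only one value can exceed it.

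| n | Cut on t | df | Formula | Simulated |
|---|---|---|---|---|
| 6 | 2.739 | 4 | 31.2% | 31.2% |
| 8 | 2.806 | 6 | 24.7% | 24.7% |
| 12 | 2.872 | 10 | 19.9% | 19.9% |
| 24 | 2.937 | 22 | 18.3% | 18.1% |

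About half of the flags are high values.

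**Effect on the primary interval, group by group, no true effect.** Simulated ANCOVA with group and weight, layouts 6/6/6/6, 12/6/6/6 and 6/6/6/3. Assumptions: CV 30%, weight SD 15 kg, slope −0.5% per kg, test iterated on unadjusted log values.

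| Use of the rule | Coverage of nominal 90% CI |
|---|---|
| Not used | about 90% |
| A quarter of groups | 88–90% |
| Half of groups | 86–88% |
| Every flag acted on | 82–85% (intervals 6–8% too narrow) |

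With a true 2-fold severe group tested only against itself, the ratio stays at about 2. If only high flags in impaired groups are acted on (6/6/6/6, no covariate), coverage is 88%, and the interval lies wholly below the truth in 7.3% of trials instead of about 5%.

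**Pooled comparison set, severe group truly 2-fold, every flag acted on.** Ranges are across independent simulation runs. The ratio is taken over trials with at least one severe value left.

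| Layout | Outcome | CV 20% | CV 30% | CV 40% |
|---|---|---|---|---|
| 6/6/6/3 | At least one severe value deleted | 41–43% | 27–29% | 19% |
| 6/6/6/3 | All three deleted | 9–10% | 1–2% | 0.3% or less |
| 6/6/6/3 | Ratio (truth 2) | 1.84–1.87 | 1.85–1.87 | 1.85–1.89 |
| 6/6/6/2 | At least one deleted | 59–61% | 31–33% | 20% |
| 6/6/6/2 | Both deleted | 31–32% | 7% | 2–3% |

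With 6/6/6/6 the effect is small: about 8–13% of trials lose a severe value, the ratio is 1.94–1.98 and coverage is 87–88%. Pooled with no true effect, coverage stays near 90%.

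**The case against.** **The test is not run on every group.** The SAP applies it to an atypical value. If a trigger is assumed, for example at least 2-fold from the geometric mean of the rest, the flag rate in clean groups of 6 falls to 0.7%, 9% and 19% at CV 20%, 30% and 40%. This stands as a limit on size: 31% is what the test does when run, and the realised deletion rate is unknown. But the SAP defines no trigger, so when to test is itself left to judgement.

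**The two wordings can be reconciled.** The procedure may be optional to start and binding once run. This is plausible for the sentence on whether to apply it. It does not fit the other preamble sentence, which says that exclusion itself is not required.

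**Primary data may be protected.** SAP 9.3.2 mentions no deletion, SAP 8 puts every dosed subject with evaluable PK data in the PK population, and complete profiles may not be removed. These points narrow the concern. They do not clearly stop one subject's AUC or Cmax from being dropped from the ANCOVA, since the between-profile section tests values of that kind.

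**Transparency is already good.** Excluded values are documented and all databased data are listed, so a reader could recompute the result. That is true, but the plan already requires both results for small groups and gives no reason to stop at six.

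**The worst figures stack assumptions.** They need pooling, 2 to 3 severe subjects, a true 2-fold effect and every flag acted on. This stands, and they should be read as conditional.

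**Conclusion.** The concern holds, and the rule is wrong as written. The contradiction, the open comparison set and the reporting gap are plain in the text and need no assumption. The 31% flag rate at n = 6 rests on normal log values, the sample SD, and the test being run on every clean group; it is an upper limit on deletion. Coverage of 82–85% applies if every flag is acted on group by group, and the loss shrinks as the rule is used less. Group by group, the ratio is not biased by symmetric use of the rule. Material loss of severe-group data arises only under the pooled reading with the 2 to 3 severe subjects that the plan accepts. This should be fixed before the primary analysis is run.

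**What to change.** Amend SAP 9.3.1 as follows.

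- State that the primary ANCOVA for AUC(0-∞) and Cmax uses all evaluable values.
- Keep the range test as a flag only, and change the last step for n ≥ 6 from exclusion to flagging. This also removes the conflict with the preamble.
- Name the comparison set, for example within hepatic group and separately for each parameter.
- Extend the existing rule for n < 6 to every n: results with and without the flagged value, both reported, with the run that omits it labelled as a sensitivity analysis.

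The cost is one SAP paragraph and one extra sensitivity table. Intervals will be slightly wider than under automatic exclusion, but they will have their stated coverage.

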9.3.2 Pharmacokinetic Statistical Methodology

The primary PK analysis is the evaluation of log-transformed $AUC(0-\infty)$ and C_{max} using an analysis of covariance (ANCOVA) model with hepatic function group as fixed factor and body weight as covariate. The geometric least squares means for each group, geometric least squares mean ratios between each hepatic impairment level versus the control group, and the corresponding 90% confidence intervals (CIs) will be estimated from the ANCOVA model. In the event of dose adjustment based on the interim analyses results, dose normalized PK parameters may be used in the above model.

Example SAS code:

```
proc mixed data=DATAIN alpha=0.1;
  by parameter;
  class group;
  model log_pk = group weight / cl residual ddfm=kr;
  lsmeans group / pdiff=control('Control') alpha=0.1;
run;
```

The analysis of t_{max} will be based on a nonparametric method. Medians and differences in medians for hepatic function groups and the p-value from a Wilcoxon rank sum test will be presented.

The relationship between the PK parameters and Child-Pugh Classification parameters (serum albumin concentration, total bilirubin concentration, and prothrombin time) will be assessed graphically. The PK parameters $AUC(0-\infty)$, C_{max} , and CL/F will be plotted against each Child-Pugh Classification parameter separately. A regression line and corresponding 90% CI from a simple linear model will be plotted, if appropriate.

Similarly, the PK parameters versus Child-Pugh Score will be assessed graphically. The control group will be kept in the analysis (with Child-Pugh score set to 0).

Additional PK parameters may be analyzed if deemed appropriate following a review of the data.

Additional exploratory analysis (such as metabolism work, protein binding, or bioanalytical method cross-validation) may be performed at a later date. Such analysis will be detailed in a separate analysis plan.

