#### **10.3.2.2. Pharmacokinetic Statistical Inference**

The primary PK analysis is the evaluation of log-transformed  $AUC(0-\infty)$  and  $C_{max}$  using an analysis of covariance (ANCOVA) model with hepatic function group as fixed factor and body weight as covariate. The geometric least squares means for each group, geometric least squares mean ratios between each hepatic impairment level versus the control group, and the corresponding 90% confidence intervals will be estimated from the ANCOVA model. In the event of dose adjustment based on the interim analyses results, dose normalized PK parameters may be used in the above model.

The analysis of  $t_{max}$  will be based on a nonparametric method. Medians and differences in medians for hepatic function groups and the p-value from a Wilcoxon rank sum test will be presented.

The relationship between the PK parameters and Child-Pugh Classification parameters (serum albumin concentration, total bilirubin concentration, and prothrombin time) will be assessed graphically. The PK parameters  $AUC(0-\infty)$ ,  $C_{max}$ , and apparent clearance will be plotted against

each Child-Pugh Classification parameter separately. An appropriate model may be fitted to the data.

Additional PK parameters may be analyzed if deemed appropriate following a review of the data.

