#### ***10.3.5. Interim Analyses***

One interim analysis is planned to occur during Study GPGQ. Two subjects each from Groups 2 and 3 (subjects with mild and moderate hepatic impairment, respectively) and at least 2 subjects in Group 1 (appropriate matched-control subjects with normal hepatic function) will be enrolled in parallel and dosed with 5 mg tirzepatide, followed by an interim analysis to evaluate safety, tolerability, and PK data. Based on this interim analysis, dosing will either continue at 5 mg or be reduced to 2.5 mg for the remainder of subjects in Groups 2 and 3 (mild and moderate impairment) and all subjects in Group 4 (severe impairment), as well as for control subjects in Group 1. The final dose determinations will be made by the investigator and the Lilly study team. If an additional unplanned interim analysis is deemed necessary, the Lilly CP, CRP, investigator, or designee will consult with the appropriate medical director or designee to determine if it is necessary to amend the protocol.

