Subjects with normal hepatic function and with mild and moderate hepatic impairment (Groups 1 to 3) can be dosed concurrently ([Figure GPGQ.1](#)). Dosing of the first subject in Group 4 (severe hepatic impairment) may proceed only after satisfactory review of safety, tolerability, and PK data from at least 2 subjects in Group 2 (mild hepatic impairment), at least 2 subjects in Group 3 (moderate hepatic impairment), and at least 2 subjects in Group 1 (appropriate matched-control subjects with normal hepatic function). Based on continuous review of safety and tolerability data, the dose of tirzepatide may be reduced to 2.5 mg for the remainder of subjects in Groups 2 and 3 (mild and moderate impairment) and all subjects in Group 4 (severe impairment), as well as for control subjects in Group 1.

Note: dosing of the first subject with severe hepatic impairment (Group 4) may proceed only after satisfactory review of safety, tolerability and PK data from at least 2 subjects with mild hepatic impairment (Group 2), and at least 2 subjects with moderate hepatic impairment (Group 3), and at least 2 subjects in Group 1 (appropriate matched-control subjects with normal hepatic function).

Figure GPGQ.1. Illustration of study design for Protocol I8F-MC-GPGQ

The total duration of study participation for each subject (from screening through follow-up visit) is anticipated to be approximately 8 weeks.

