10. INTERIM ANALYSES

One interim analysis is planned to occur during Study GPGQ. Two subjects each from Groups 2 and 3 (subjects with mild and moderate hepatic impairment, respectively) and at least 2 subjects in Group 1 (appropriate matched-control subjects with normal hepatic function) will be enrolled in parallel and dosed with 5 mg tirzepatide, followed by an interim analysis to evaluate safety, tolerability, and PK data. Based on this interim analysis, dosing will either continue at 5 mg or be reduced to 2.5 mg for the remaining subjects subjects in Groups 2 and 3 (mild and moderate impairment) and all subjects in Group 4 (severe impairment), as well as for control subjects in Group 1. The final dose determinations will be made by the investigator and the Lilly study team.

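### If the interim leads to a dose cut, does optional dose normalisation leave the severe-versus-control PK ratios unprotected?

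*SAP*

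**What the plan says.** - **The dose branch.** Two mild, two moderate and at least two control subjects "will be enrolled in parallel and dosed with 5 mg tirzepatide, followed by an interim analysis to evaluate safety, tolerability, and PK data" (Protocol 10.3.5). After that, "dosing will either continue at 5 mg or be reduced to 2.5 mg" for the remaining mild and moderate subjects and for "all subjects in Group 4 (severe impairment), as well as for control subjects in Group 1" (SAP 10). Group 4 cannot start before this review (Protocol 5.1, SAP 5).
- **Order of dosing.** "Subjects with normal hepatic function and with mild and moderate hepatic impairment (Groups 1 to 3) can be dosed concurrently" (SAP 5). No upper limit is put on the number of controls dosed before the interim.
- **The primary model.** Log AUC(0-∞) and log Cmax on group and weight, with 90% confidence intervals and no dose term (SAP 9.3.2).
- **The remedy.** After a dose adjustment, "dose normalized PK parameters may be used in the above model" (Protocol 10.3.2.2). SAP 9.3.2 carries the same sentence: "In the event of dose adjustment based on the interim analyses results, dose normalized PK parameters may be used in the above model".
- **A dose-adjusted parameter.** CL/F is in the parameter list of SAP 9.3.1. In SAP 9.3.2 it appears with AUC(0-∞) and Cmax: "and CL/F will be plotted against each Child-Pugh Classification parameter separately".
- **Labelling and safety.** "The TFLs will include a subheader for treatment (5 mg tirzepatide SC) throughout" (SAP 6). Treatment-emergent adverse events are tabulated by group, all adverse events are listed, and no inferential safety analysis is planned (SAP 9.5.1, 9.5.11).

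**The concern.** The interim is planned and the cut is one of its two named outcomes, so the primary analysis for that outcome could have been fixed in advance. As written, two different analyses remain open in an open-label study.

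The direction of the error matters. One reason given for a cut is exposure in impaired subjects above what was expected (Protocol 5.5 and 7.4). Comparing a severe group at half the dose with controls partly at full dose pulls the ratio down, towards hiding that same signal. The study's purpose is to learn whether impaired patients can be given the drug without dose adjustment, so a low ratio would mislead. Mixing doses within groups also inflates the residual variance.

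After a cut, a severe group at 2.5 mg would also appear under a 5 mg heading in the adverse event tables, beside controls some or all of whom had 5 mg.

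**Working it through.** **The plan's own figure.** Group maxima or targets of 12 + 6 + 6 + 6 give 30, the stated maximum enrolment. No power, effect size or SD is given, so there is nothing else to reproduce.

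**Bias without normalisation.** Inputs: all of Group 4 at 2.5 mg and *k* of *n* controls at 5 mg (SAP 10), with *n* from 6 to 12 (SAP 5). Assumption: exposure proportional to dose, which the documents do not state. On the log scale the control mean rises by (*k*/*n*) × ln 2, so the severe/control ratio is multiplied by 2^(−*k*/*n*).

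| Controls at 5 mg | Factor | A true 1.5 shows as |
|---|---|---|
| 2 of 12 | 0.891 | 1.34 |
| 2 of 6, or 4 of 12 | 0.794 | 1.19 |
| 4 of 6 | 0.630 | 0.94 |
| all | 0.500 | 0.75 |

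The planned sequence puts two mild and two moderate subjects before the interim. One-to-one matching then calls for two controls if each is shared across the two groups, or four if none is. Two of a final 6 and four of a final 12 are both one third, giving 0.79. The last two rows need a larger share of controls dosed early. The text permits this, but it runs ahead of the matching.

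For mild or moderate subjects with 2 of 6 at 5 mg, the factor is 2^(2/6 − *k*/*n*): 1.00 with 2 of 6 controls at 5 mg and 1.12 with 2 of 12.

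**Interval width.** Take 6 per group, 2 of 6 at 5 mg in Groups 1 to 3, and an assumed between-subject CV of 30%.
- Log variance: ln(1 + 0.3²) = 0.0862.
- Dose mixing adds (ln 2)² × (2 × 4/6) = 0.641 to the sum of squares in each of three groups. Over 24 − 5 = 19 df this is 3 × 0.641/19 = 0.101.
- Half-width factor, normalised: exp(1.729 × √0.0862 × √(1/6 + 1/6)) = 1.34.
- Half-width factor, raw: exp(1.729 × √(0.0862 + 0.101) × √(1/6 + 1/6)) = 1.54.

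**Coverage of the true ratio.** The planned ANCOVA was simulated with log-normal exposure, weight unrelated to exposure and CV 30%, using 4,000 to 5,000 trials per case.

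| Case | Raw | Normalised |
|---|---|---|
| 2 of 6 controls at 5 mg, 6 severe | 0.86 | 0.90 |
| 2 of 12 controls, 6 severe | 0.93 | 0.90 |
| 2 of 6 controls, 2 severe | 0.94 | 0.90 |
| 4 of 6 in each of Groups 1–3, 6 severe | 0.42 | 0.89 |
| all 6 controls, 2 of 6 in Groups 2–3, 6 severe | 0.05 | 0.90 |

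The raw interval loses little coverage at the planned minimum. With 12 controls or only 2 severe subjects it over-covers, because dose mixing widens it. The point estimate is still biased in those cases. Serious under-coverage appears only when most controls had 5 mg.

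**What is reported anyway.** CL/F is dose divided by AUC(0-∞), so dose-normalised AUC is its reciprocal. A rise in dose-adjusted AUC in severe impairment would show as a fall in CL/F in the planned plots, whichever form the ANCOVA takes. Cmax has no such counterpart, and no group ratio with an interval is specified for CL/F.

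**The case for a change.** The best case for a change is that the branch is foreseeable, the SAP is to be signed before first dosing, and one verb would settle which analysis is primary. The bias runs in the unsafe direction, and the text sets no cap on controls at 5 mg, so factors of 0.63 or 0.50 cannot be excluded. The normalisation sentence is also tied to the interim, whereas Protocol 5.1 and SAP 5 allow a reduction from ongoing safety and tolerability review.

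The arithmetic stands, and a stated default would have been tidier. What does not stand is that the plan leaves the analyst without direction. Both documents name normalisation, and only normalisation, for a dose adjustment, and the same reasoning applies to any mid-study dose change. No hypothesis test, no-effect boundary or power target depends on the choice.

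A firm rule also has a price, because it fixes a proportionality assumption that the documents do not support with data. The available checks are weak. With a dose term, the half-width factor is 1.36 against 1.34 when each of Groups 1 to 3 has 2 of 6 at 5 mg. It rises to 1.54 when all six controls had 5 mg and Groups 2 and 3 are split two and four. If Groups 1 to 3 were all at 5 mg, the dose term cannot be estimated.

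On labelling, a 5 mg heading over 2.5 mg data would be wrong. It is a clerical matter for table shells held in a separate document (SAP 3). The adverse event tables are descriptive, though after a cut they would need the actual dose beside them to be read properly.

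Separately, the sections on what prompts a dose reduction do not match. Protocol 5.1 and SAP 5 refer to safety and tolerability. Protocol 5.5, 7.4 and 10.3.5 and SAP 10 also bring in PK. The sponsor should reconcile them; no view is taken here on which should stand.

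**Conclusion.** No change to the analysis plan follows. The gap is real but small: a permissive verb attached to the right remedy, in the right paragraph, for the branch in question. Harm requires a dose cut and then an unnormalised primary analysis. If dosing stays at 5 mg, nothing is affected.

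If both events happened, the severe/control ratio would be multiplied by about 0.79 to 0.89 on the planned interim sequence, and by less than that only if more than about a third of controls had 5 mg. These factors assume dose proportionality. The interval results also assume a between-subject CV (30% in the figures shown), since the documents give none. A statistician with mixed doses in hand would normalise, and would correct the table heading, without being told to.
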